## 2. Background

Near-infrared spectroscopy (NIRS), is a technology that can provide continuous, non-invasive monitoring of oxygenation in tissue[1]. Light absorption is measured at a few discrete wavelengths which can provide information for the tissue oxygen saturation in multiple organs[2], with cerebral, renal and splanchnic oxygenation being the most commonly measured in neonates[1]. NIRS technology was first available in 1977, however different sensors and manufacturers resulted in a large range of regional oxygen saturation (RSO2), making it difficult to establish normative values within a specific population[1]. Thus, improvements in the technology has resulted in the ability to consider more clinical uses for the NIRS technology.

Infants with congenital heart disease is a population in which the NIRS technology has been applied. The use of cerebral oximetry measurement has provided the first indication of a clinical problem in 23% of the procedures in which the technology was utilized[1]. While some initial studies have shown a negative correlation between cerebral regional oxygen saturation (cRSO2) and gestational age[3], routine use in the preterm infant has not been established.

Infants born prematurely (<37 weeks’ gestation), and especially those born extremely preterm (<28 weeks’ gestation), have organs that are immature and vulnerable. There are fluctuations in cerebral blood flow due to limitations in autoregulation, which may be exacerbated by routine care of the infant[4]. Previously there was a limitation in the ability to monitor these changes in blood flow and saturations, however NIRS now provides the technology needed. There are clinical trials ongoing to assess cRSO2 immediately after birth in an attempt to improve outcomes[5] as well as monitoring in the first 72 hours of life in extremely preterm infants[4]. While these studies will likely provide support for applying NIRS as routine care for preterm infants, there is data lacking when infants are born at altitude. It is unknown if the increased altitude in places such as Albuquerque and Denver would result in a different range of expected values with NIRS monitoring. Thus, we proposed a prospective observational study in which we apply NIRS monitoring to

PROTOCOL TITLE:

infants born <32 weeks' gestation for the first 96 hours of life to assess the cRSO2 as well as outcome information for the infant.

### **3. Study Design**

The study will be a prospective observational study, in which any infant consented to participate in the study will have the NIRS applied for the first 96 hours of life. It will be the goal to apply the NIRS sensors in the first 12 hours of life. All infants will have the same treatment if in the study, but clinicians will not be able to see the data obtained so that there is no clinical interpretation during this time.

### **4. Inclusion and Exclusion Criteria**

#### Inclusion Criteria:

- Infant must be <32 weeks' gestational age at time of delivery.
- Consenting mother/guardian of the infant must speak English. Other languages are not being included due to the need of a translator being brought into the unit, which adds risk to the vulnerable population. Additionally, as the time to consent is a narrow window, adding the complexity of getting a translator may delay the ability to get consent and thus make it more difficult to enroll patients.
- Infants that require blood transfusions during the monitoring time may be included.

#### Exclusion Criteria:

- Any known cardiac anomaly or other anomaly which may impair perfusion and blood flow.
- Infant born after placental abruption or concern for extreme blood loss immediately after birth.
- Unable to consent the mother/guardian due to maternal health issues after delivering (eg requiring intubation or sedation after the delivery).
- Mothers/guardians that are prisoners, as the study team would like to have continuing communication with the mother during the study period as needed.
- Mothers/guardians that are <18 years of age will not be approached for consent.
- Any mother/guardian that is not able to consent due to having a legal representative will not be approached for consent in this study.
- Any infant that is planned to be placed for adoption
- Infant is greater than 24 hours of age at time of consent.

Individuals will be screened for eligibility by reviewing the Newborn Intensive Care Unit (NICU) census twice daily.

Any infant that has been consented for participation and completes at least 48 hours of NIRS monitoring will be included in the final study sample.

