## 1. Objectives

The objective of this study is to obtain the cerebral regional oxygen saturation (cRSO2) in a preterm population that is born at altitude to determine if the range of “normal” values is different than those obtained at sea level. **We hypothesize that the cRSO2 will be lower than the normative values that have been previously described.** As more clinical studies are being performed, and the use of NIRS becomes more common, it is imperative that we assess if other factors such as altitude must be considered prior to general implementation.

**Aim 1:** We will prospectively obtain cRSO2 for the first 96 hours of life in infants born <32 weeks’ gestation. The data obtained will not be interrupted clinically as the clinicians will not be able to view the data obtained from the NIRS monitoring.

**Aim 2:** Outcome measures including death, intraventricular hemorrhage, necrotizing enterocolitis, sepsis, duration of supplemental oxygen required, time to taking full volume feeds via nipple, and hospital length of stay will be collected. This will be compared with the infant’s average cRSO2 as well as the fluctuation in cRSO2 that was observed. This may provide supportive evidence for clinical use of NIRS in future trials at UNMH.

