### **15.Withdrawal of Subjects**

If at any time there are concerns that the NIRS is interfering with routine care (although not expected to occur), the subject will be withdrawn from the research without their consent. If withdrawal from the study needs to occur, the NIRS equipment will be removed and any data collected to that point will be utilized. Collection of information will be obtained from the medical record as previously described, even if the NIRS monitoring is discontinued early. A subject can voluntarily withdrawal at any time from the study with no consequence or change in routine medical management. If a parent decides to withdraw the participant from the study, then any data that has already been collected will be kept for analysis (unless the PI is contacted as described in the next sentence). If the parent / guardian wishes to remove the data collected, then they can contact the PI , [name], at [contact] to request all data to be removed and it will be removed. No additional data will be collected.

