### **17.Data and Specimen Banking – N/A**

### **18. Risks to Subjects**

We expect the risks to the subjects to be minimal in relation to the NIRS device. The infants in this study, particularly in group 1, are at high risk of serious adverse events not related to NIRS. Specifically, this gestational age group is at high risk of death, severe brain injury, necrotizing enterocolitis, chronic lung disease, retinopathy of prematurity and sepsis. These will be included as outcome measures for the assessment, but the presence of any of these conditions would not be related to the use of NIRS.

The risks that may be present related to NIRS sensor placement include erythema and irritation of the skin around the sensor. If this is noted, the sensor will be removed. If the area appears to have erythema and/or irritation after removal, no sensor will be replaced, and the data collected to that point will be used in analysis. We will use adhesive remover or a warm moist cloth to gently remove the sensor to avoid any discomfort during this process.

As protected health information will be gathered, there is the risk for loss of privacy and/or confidentiality. We will minimize these risks by giving each participant a study ID and removing the identifiers at that time. Per policy, records of participants under the age of 18 years must be stored until the youngest participant receives 22 years of age. All records will be stored either electronically on [name] UNM issued password protected computer that is stored in her locked office, or paper copies will be stored in a locked cabinet in [name] office in BRF137D.

PROTOCOL TITLE:

Additionally, there is the possibility of unforeseen risks. Any concerns or SAE from the study will be reported to the IRB immediately.

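### Section 4 ties the final sample to at least 48 h of NIRS, Sections 15 and 18 send shorter recordings to analysis, and Section 13 does not say which governs; the 48 h rule also selects Aim 2 on survival

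*Combined protocol and SAP*

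**What the plan says.** The only definition of the final sample is at the end of the exclusion criteria in Section 4. A consented infant who "completes at least 48 hours of NIRS monitoring will be included in the final study sample". The sentence does not say that other infants are excluded.

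Three later statements deal with infants whose monitoring stops early. None gives a minimum duration or mentions 48 h.

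- Section 15, when withdrawal needs to occur: "the NIRS equipment will be removed and any data collected to that point will be utilized".
- Section 15, withdrawal by a parent: "any data that has already been collected will be kept for analysis", unless the parent asks for removal.
- Section 18, irritation still present after the sensor is taken off: "no sensor will be replaced, and the data collected to that point will be used in analysis".

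Section 13 averages cerebral saturation for each infant and summarises NIRS parameters by median and interquartile range. It names no analysis set and does not repeat the 48 h threshold. Its only population wording refers to enrolled infants, for the gestational-age sub-analysis.

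Section 1 lists the Aim 2 outcomes: "Outcome measures including death, intraventricular hemorrhage, necrotizing enterocolitis, sepsis" and others. They are to be compared with each infant's average saturation and its fluctuation.

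On follow-up, Section 15 says: "Collection of information will be obtained from the medical record as previously described, even if the NIRS monitoring is discontinued early". After the text on parental withdrawal, and directly after the sentence on asking the investigator to remove data, it says: "No additional data will be collected".

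**The concern.** A 48 h condition on the final sample has its natural meaning only if some infants with less are left out. Sections 15 and 18 nevertheless send recordings of any length to analysis for two groups who may well have less than 48 h. Two analysts following the same protocol could analyse different infants, and the choice could be made with the results in view. The main product is a median and interquartile range, so sample membership bears directly on it.

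The second problem concerns Aim 2. Completing 48 h of recording requires surviving long enough to do so. If the 48 h set is used to relate saturation to death, the earliest deaths are removed by construction. Section 18 itself describes the youngest group as being at high risk of death and severe brain injury, so some early losses are foreseeable.

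**Working it through.** The plan has no figure of its own to reproduce on this point. The check is a comparison of the text, followed by arithmetic on timing and an illustration of size.

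**Which rule covers an infant with under 48 h of NIRS**

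| Reason for the short recording | Section 4 | Sections 15 and 18 |
|---|---|---|
| Withdrawal because NIRS interferes with care | not in the final sample, on its natural reading | data used (Section 15) |
| Withdrawal by a parent, no removal request | same | data kept for analysis (Section 15) |
| Persisting skin irritation | same | data used (Section 18) |
| Death while still monitored | same | not addressed |

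The first three rows have competing rules. The last has only Section 4. Section 13 settles none of them.

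**Timing**

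Inputs: 48 h threshold (Section 4); end of monitoring at 96 h of age (Sections 3, 6 and 12); placement goal within 12 h of birth (Section 3); age at consent at most 24 h (Section 4), with the device applied after consent (Section 6).

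Earliest qualifying age = age at placement + 48 h:

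- placed close to birth: about 48 h
- placed at 12 h: 12 + 48 = 60 h
- placed at 24 h: 24 + 48 = 72 h; because 24 h is the limit for consent, placement can be slightly later

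So no death before about 48 h of age can be in the 48 h set, and for later placement the cut-off is later.

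Recording that can be lost before an infant falls below 48 h = 96 − age at placement − 48: 48 h if placed at birth, 36 h if placed at 12 h and 24 h if placed at 24 h.

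**Illustrative size**

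The documents give no rate of short recordings. Assume k short recordings among 100 infants (100 is the recruitment goal in Section 5), and take the extreme case in which all k are lower than every other recording. Quantile q of the all-data set then sits at (100q − k)/(100 − k) in the 48 h set. The conversion to SD assumes normality.

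| k | Median | Shift | Lower quartile | Shift |
|---|---|---|---|---|
| 5 | 45/95 = 47.4% | 0.066 SD | 20/95 = 21.1% | 0.130 SD |
| 10 | 40/90 = 44.4% | 0.140 SD | 15/90 = 16.7% | 0.293 SD |

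If all the short recordings were the highest, the shift would be mirrored at the upper quartile. If they were scattered, it would be smaller.

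Loss of precision is minor. Leaving 95 or 90 of 100 infants widens a confidence interval by a factor of √(100/95) = 1.026 or √(100/90) = 1.054.

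**The case against.** The strongest reply is that the sections can be read together. Section 4 says who will be included, not that only they will be. Sections 15 and 18 may be specific provisions that add two groups, while the 48 h condition still governs recordings cut short by death, signal loss or long gaps. This stands in part. A reader might infer a flat contradiction, with a short recording both in and out of the sample. The wording does not go that far. But no section refers to the other, and Section 13 does not choose, so the reconciling reading is one option among several. That reading also confirms that early deaths are left to Section 4 alone.

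A minimum recording length is also defensible when the aim is a normal range. That stands, and the fix allows for it. It does not carry over to Aim 2, where death is an outcome.

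A reader might further infer that every infant withdrawn by a parent loses later outcomes, because Section 15 ends that passage with "No additional data will be collected". The sentence directly follows the option to "request all data to be removed and it will be removed" and may apply only to that case. The earlier sentence on continued chart collection is not limited by reason for stopping. The text is ambiguous, which calls for clarification and does not establish a loss of outcomes.

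Finally, this is an observational pilot, the plan does not expect skin problems or interference with care to be common, and the illustrated median shifts are small. That limits the weight of the point but does not remove it.

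**Conclusion.** The point holds. For withdrawn and skin-reaction infants with under 48 h, the plan has competing statements and nothing to decide between them. For infants who die before completing 48 h of recording, Section 4 is the only rule and leaves them out, so Aim 2 would be selected on survival. Deaths before about 48 h of age can never enter the 48 h set; with placement at 12 h or 24 h the cut-off is 60 h or about 72 h.

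The documents give neither the number of infants affected nor the direction of bias. The shifts of 0.07 or 0.14 SD in the median and 0.13 or 0.29 SD in the lower quartile rest on an assumed 5 or 10 short recordings per 100, all at one extreme, and on normality. A reader might take them as upper limits on the bias. They are limits only for those counts, and more short recordings would allow larger shifts. They describe the saturation summary and say nothing about the size of any bias in the comparison with death. This should be corrected before analysis; it does not threaten the feasibility of the study.

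**What to change.** Reconcile Sections 4, 15 and 18 in one analysis-set statement in Section 13, fixed before the data are seen.

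- **Saturation range:** the 48 h set may stay primary, with the all-data set also reported.
- **Aim 2, at least for death:** include all consented infants with any usable NIRS data, except data removed at a parent's request, and report the 48 h set alongside. Define usable in advance.
- **Fluctuation:** this is hard to compare across unequal durations, so the 48 h set may be kept as primary.
- **Reporting:** give the number of infants under 48 h by reason (death, skin, interference with care, parental withdrawal, other) and by gestational-age group.
- **Section 15:** say whether the stop on further data collection applies to all parental withdrawals or only to data-removal requests. Count infants without later outcomes as missing for Aim 2, not as silently dropped.

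The cost is a few sentences of protocol text and an extra table, with no added infants or procedures. The downsides are that short recordings are noisier and that a recording made shortly before death may reflect dying and not predict it. Reporting both sets lets readers judge how much either matters.

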### **5. Number of Subjects**

PROTOCOL TITLE:

This is a single site, observational study. The goal number of patients to be recruited is 100. A similar study that evaluated an older cohort (30 weeks' gestation to 42 weeks' gestation) was able to find significant differences with a sample size of 100[3]. Given the number of extremely preterm infants (<28 weeks' gestation) born at UNMH varies from 18-30 per year, we expect to reach goal enrollment within a 2-year period, as we are including up to 32 weeks' gestation.

## 6. Study Timelines

An individual will participate in the study if the guardian consents for participation. The NIRS device will be applied after consent has been obtained (ideally within the first 12 hours of life). The device will remain in place, with routine skin care management during care times, for the first 96 hours of life and then removed. No further interventions will occur during the study period. Data on relevant outcomes will be extracted from the hospital chart during the birth hospitalization.

The duration of time to enroll subjects is 2 years. If the goal enrollment is reached sooner, then enrollment will be stopped. Upon completion of enrollment, data will then be analyzed. This is expected to be completed 6 months after enrollment is complete; thus, the study duration is expected to be 2.5 years.

## 7. Study Endpoints

The primary endpoint of the study will be upon completion of goal enrollment of 100 infants. During the enrollment period, a safety review will be completed every 5 subjects to ensure there are no adverse effects from the NIRS equipment. Specifically, skin integrity will be assessed. Given the use of this technology in multiple other studies at this gestational age, this is not expected to be a common finding. However, this will be routinely checked. Additionally, a data safety monitoring board (consisting of neonatologist [name] and co-investigators) will review the findings every 10 infants to ensure no safety concerns exist; any concerning findings will be immediately reported to the IRB (please see section 14 for additional information).

At this time, no exploratory endpoints are expected beyond the Aims presented.

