### **13.Data Analysis**

The cerebral regional oxygen saturation data will be averaged for each infant. All male and female data will be analyzed separately and the compared to determine any statistical differences that are present between sexes. NIRS parameters will be summarized as median and interquartile ranges. The relative cerebral fractional tissue oxygen extraction will be calculated using the following equation:  $(SpO_2 - rScO_2)/SpO_2$ .

As described above, there will be a sub-analysis of the infants enrolled based on gestational age. Specifically, the 3 groups will be divided into the following ages: Group 1: 23 to  $\leq 26$  weeks' gestation; Group 2:  $>26$  weeks' gestation to  $\leq 29$  weeks' gestation; Group 3:  $>29$  weeks' gestation to 31 6/7 weeks' gestation. Comparisons among different groups will be analyzed by one-way ANOVA followed by Dunn's method. Categorical data will be analyzed using Fisher's test. Spearman's rank correlation coefficient will be used to calculate correlations between cerebral regional oxygen saturation, relative cerebral fractional tissue oxygen extraction and gestational age. Values of  $p < 0.05$  will be considered statistically significant.

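### The altitude hypothesis has no planned comparison: the primary endpoint is an enrolment milestone, no sea-level reference is named, and every planned comparison is within the cohort

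*Combined protocol and SAP*

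**What the plan says.** - **Objective and hypothesis (section 1).** The study is to find out whether the range of normal "values is different than those obtained at sea level". The hypothesis is that cRSO2 "will be lower than the normative values that have been previously described". No value, citation, device, gestational age or postnatal age is attached to those norms.
- **Endpoint (section 7).** "The primary endpoint of the study will be upon completion of goal enrollment of 100 infants". The section adds that nothing exploratory is expected beyond the Aims.
- **Analysis (section 13).** "The cerebral regional oxygen saturation data will be averaged for each infant", and "NIRS parameters will be summarized as median and interquartile ranges". The comparisons are male against female, three gestational-age groups ("there will be a sub-analysis of the infants enrolled based on gestational age"), Fisher's test for categorical data, and Spearman correlations among cRSO2, oxygen extraction and gestational age. Significance is set at p < 0.05.
- **Aims (section 1).** Aim 1 is to obtain cRSO2 for the first 96 hours of life. Aim 2 relates clinical outcomes to each infant's own average cRSO2 and its fluctuation.
- **Sample size (section 5).** The study is single-site with a goal of 100. The support given is "A similar study that evaluated an older cohort", of 30 to 42 weeks' gestation, which found significant differences with 100 infants.
- **Background (section 2).** Differences between sensors and manufacturers are said to have produced a wide spread of values. The section also reports that "some initial studies have shown a negative correlation between cerebral regional oxygen saturation" and gestational age, citing the same study that section 5 uses.

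**The concern.** The one hypothesis is about a difference from sea level, so it needs an outcome, a reference and a contrast between them. The stated primary endpoint supplies none of these, and the analysis section supplies only the per-infant measure.

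The protocol does not say when or how a reference would be picked. It could therefore be picked once the cohort's values are known. Section 2 itself names two features, sensor and gestational age, on which published values vary. An unadjusted comparison with a norm chosen late could mix altitude with either of them, and the conclusion could depend on which norm was chosen.

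**Working it through.** **1. Does any planned analysis use an external value?**

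| Place | Analysis | External or sea-level value used? |
|---|---|---|
| Section 13 | Per-infant average; median and IQR | No |
| Section 13 | Male against female | No |
| Section 13 | Three gestational-age groups | No |
| Section 13 | Fisher's test, categorical data | No |
| Section 13 | Spearman correlations | No |
| Section 1, Aim 2 | Outcomes against own cRSO2 and its fluctuation | No |
| Section 7 | Enrolment of 100 | No, and not an outcome |

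The study is single-site, so there is no concurrent sea-level group either. The objectives, sample-size, endpoint and analysis sections are all present in the public text, so removed pages do not explain the gap.

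**2. Is the section 5 study the reference by implication?** It is cited there only to justify the number of infants. It covered 30 to 42 weeks, and this cohort is below 32 weeks, so the two overlap only from 30 to 31 6/7 weeks. The documents give neither its altitude nor its cRSO2 values. Nothing designates it as the norm.

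**3. Can the plan's own figure be reproduced?** No. The goal of 100 comes with no effect size, SD, power, sidedness or reference, so there is nothing to recompute for the altitude question.

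**4. Scale, on assumptions.** Take n = 100 infants here (section 5). Assume an SD of 5 to 10 points, equal in both cohorts, and a reference of m = 100.

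- Unadjusted half-width = 1.96 × SD × √(1/n + 1/m) = 1.96 × SD × √0.02 = 0.277 × SD. This is 1.39 points at SD 5 and 2.77 at SD 10.
- If the published mean were treated as exact: 1.96 × SD × √(1/100) = 0.196 × SD, or 0.98 to 1.96 points. Ignoring the reference's sampling error makes the interval too short by a factor of √2 = 1.41 when m = 100.
- Standardised to the reference's gestational-age mix, 1/n becomes D/n, where D = Σ(w²/p), p is the share of this cohort in each group and w is the reference's share. D equals 1 only when the two mixes match and otherwise exceeds 1. At the same SD the interval is therefore wider than the unadjusted one. The documents give neither mix, so the amount cannot be stated.
- For the range, the 5th percentile under normality has half-width 1.96 × SD × √(1/100 + 1.645²/(2 × 99)) = 0.302 × SD, or 1.5 to 3.0 points.

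**The case against.** The strongest reply is that this is a descriptive pilot. The funding section calls it one, Aim 1 is simply to obtain cRSO2, and section 13 does plan an estimate of it. The section 7 sentence can be read as loose template wording for when the study ends, and its pointer to the Aims suggests that cRSO2 was always the intended measure.

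Part of this stands. A reader might infer that the plan contains no estimate at all. That goes too far, because the per-infant average with median and IQR is a planned estimate for the cohort. cRSO2 is also a fair guess at the intended outcome. But neither Aim contains the sea-level contrast, so reading the endpoint generously still leaves the hypothesis without an analysis. A pilot label excuses low precision. It does not supply a missing comparison.

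Three other stronger readings are not supported:

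- **That an older reference would bias the result by a known amount.** Section 2 reports only the sign of a correlation. The documents give no slope and do not show that it extends below 30 weeks. Section 2 also says the technology has improved, without saying that sensor differences have gone.
- **That the study is too imprecise.** The documents give no SD, target difference or reference size against which to judge that.
- **That the 48-hour rule is flatly contradicted.** Section 4 limits the final sample to infants with at least 48 hours of monitoring, while sections 15 and 18 say data up to early removal will be used. These can be read together, with pre-removal data used only for infants who reach 48 hours. The text is ambiguous, and the issue is separate from the missing comparison.

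**Conclusion.** Wrong as written. The plan states a directional hypothesis about altitude, gives an enrolment count as its primary endpoint, names no reference, and specifies only within-cohort comparisons. Carried out exactly, it would describe cRSO2 in this cohort and leave its only hypothesis unanswered. That conclusion rests on the text alone.

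The documents allow no measured size for the defect. The 1.4 to 2.8 point half-width shows what an unadjusted comparison might deliver if the SD is 5 to 10 points and both cohorts have 100 infants. A reference that is smaller, or whose gestational-age mix differs, would give a wider interval. It is also not established that a reference will be chosen after the data are seen. The point is that nothing in the protocol prevents it.

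**What to change.** 1. **Section 7.** Replace the enrolment milestone with each infant's mean cRSO2 over the monitored hours up to 96 hours of life. Keep completion of enrolment as a timeline item in section 6.
2. **Section 13, before enrolment.** Name one sea-level reference comparable on gestational age, postnatal age and, as far as possible, sensor. Record its mean, SD and n. Say explicitly whether the section 5 study is that reference. Pre-specify one whole-cohort difference, adjusted for or standardised to gestational age, with a 95% CI that includes the reference's sampling error. Standardised, the estimate is Σ w × (group mean here) − reference mean, with SE = √(Σ w² × s²/n_group + s_ref²/m). Leave the gestational-age groups as the sub-analysis that they already are. If no comparable reference exists, report descriptively and draw no altitude conclusion.
3. **Section 13, range.** Because the objective concerns a range, add the 5th and 95th percentiles with 95% CIs to the median and IQR.
4. **Separately,** reconcile sections 4, 15 and 18 in one analysis-set rule that says whether infants with under 48 hours of data enter the analysis.

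The cost is protocol wording and a reference search before enrolment. Matching the reference's sensor may also constrain the monitor and probes, which section 12 says are still to be bought. No extra infants or measurements are needed. The documents do not show that a comparable reference exists, so the altitude question may stay unanswered, but openly so.
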